7.9 Definitions

7.9.1 Baseline

Baseline is defined as the last non-missing value available before randomisation (for control group)/first treatment dose (for poractant alfa group).

Change from baseline will be derived as follows:

Assessment value at the timepoint - Assessment value at baseline

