6.2.3 Administration

Before treatment, patients transiently will receive 100% oxygen.

Poractant alfa boluses, 30 mg per kilogram of lean body weight, will be administered through a sterile syringe connected to an opaque catheter inserted into the endotracheal tube with the distal end approximately 1cm above the carina. The first half of the dose will be administered during a pause in mechanical ventilation in which PEEP will be maintained and the patient will be in the left or right lateral decubitus position, and the second half will be administered similarly 5 minutes later, with the patient in the opposite lateral decubitus position [20].

When possible, tube suctioning should be avoided for 3 hours after the administration.

Patients will receive a total of three administrations, 24 hours apart.

For details on study medication dosage and administration please refer to the IMP Management manual.

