6.6 Treatment Code

Study drug will be packaged and uniquely numbered. Each primary packaging in the medication kit will have a numbered label that matches the kit number on the label of the outside packaging.

This is an open-label study.

An individual randomization code envelope will be supplied to the Investigator for each patient and will contain the assignment treatment group for that patient. The Investigator will keep the treatment code envelopes in a locked, secure storage facility. Allocation of each patient to the assigned treatment group will be performed after opening the individual envelope associated with the lowest randomisation number.

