7. STUDY PLAN

7.1 Study Schedule

	ICU stay period					ICU discharge	Last FUP
Poractant alfa treated group	Screening ⁷	Day 1 (Randomisation)	Day 2	Day 3	Day 4 – 27	Day X	Day 28
		Before randomisation/treatment and 6-12-24h after each administration up to 72 hours			Every 24h till ICU discharge	Whenever it occurs	
Control group	Screening	Time 72 h			Day 4 – 27	Day X	Day 28
		Before randomisation and at 6, 12, 24, 30, 36, 48, 54, 60, 72 h since randomisation			Every 24h till ICU discharge	Whenever it occurs	
Assessments							
Informed consent	X						
Inclusion and exclusion criteria	X						
Demography	X						

Clinical Study Code No.: CLI-050000-04	Version No.: 4.0
EUDRACT No.: 2020-002632-75 – IND No: 153286	Date: 02 MAR 2021

Poractant alfa treated group	ICU stay period					ICU discharge	Last FUP
	Screening ⁷	Day 1 (Randomisation)	Day 2	Day 3	Day 4 – 27	Day X	Day 28
		Before randomisation/treatment and 6-12-24h after each administration up to 72 hours			Every 24h till ICU discharge	Whenever it occurs	
Control group	Screening	Time 72 h			Day 4 – 27	Day X	Day 28
		Before randomisation and at 6, 12, 24, 30, 36, 48, 54, 60, 72 h since randomisation			Every 24h till ICU discharge	Whenever it occurs	
Vital signs (blood pressure, heart rate)	X	Once Treated group: 24 - 48 - 72h post start of treatment Control group: 24 - 48 - 72h post randomisation			X	X	X
Full physical examination including height and weight	X						
Medical history (SARS COVID-19 ADRS, past and current relevant medical conditions)	X						
Arterial Blood Gas (ABG) Analysis ¹	X (If the screening assessment is done just before randomization no need to repeat the assessment)	Treated group: Before randomisation and 6-12-24h after each administration up to 72 hours Control group: Before randomisation and at 6, 12, 24, 30, 36, 48, 54, 60, 72h since randomisation			Every 24h	X	Once if not discharged from ICU
Respiratory support assessment Ventilator parameters ²	X (If the screening assessment is done just before randomization no need to repeat the assessment)	Treated group: Before randomisation and 6-12-24h after each administration up to 72 hours Control group: Before randomisation and at 6, 12, 24, 30, 36, 48, 54, 60, 72h since randomisation			Every 24h	X	Once if not discharged from ICU

Clinical Study Code No.: CLI-050000-04	Version No.: 4.0
EUDRACT No.: 2020-002632-75 – IND No: 153286	Date: 02 MAR 2021

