In case the patient will be assigned to the poractant alfa treated group, the treatment must start soon after the randomization (max 2 hr), and within 48hr after intubation

The following procedures for treated group or for control group will be conducted according to the frequencies reported in the above flowchart:

- Treatment procedure for poractant alfa as described in detail in [section 6.2](#). One administration per day with a 24 hours interval
- Arterial Blood Gas (ABG) Analysis
- Ventilatory support
- Ventilatory parameters: PaO₂/FiO₂, FiO₂, tidal volume (TV), respiratory rate (RR), static compliance (Cstat), dynamic compliance (Cdyn), PEEP (positive end-expiratory pressure), PIP (peak inspiratory pressure), Plateau Pressure (Pplat)
- Laboratory assessments for mechanistic analysis: blood sampling and bronchial washings; bronchoscopic washings performed as clinically indicated only, with surplus samples retrieved for mechanistic study as available (for more details ref. to [section 7.2](#))

Clinical Study Code No.: CLI-050000-04	Version No.: 4.0
EUDRACT No.: 2020-002632-75 – IND No: 153286	Date: 02 MAR 2021

- Laboratory assessments: blood count, bilirubin, creatinine, eGFR, LDH, D-dimer, CRP, procalcitonin
- Vital signs will be obtained as appropriate
- SOFA score is calculated considering PaO₂/FiO₂, Glasgow coma scale, mean arterial pressure, and bilirubin, platelet and creatinine levels
- AEs review (including SAEs)
- Concomitant medications and procedure review as applicable

7.1.3 Day 4 – 27 recording:

The following procedures for treated group or for control group will be conducted according to the above flowchart

- Arterial Blood Gas (ABG) Analysis
- Ventilatory support: extubation date recorded (as applicable) and following ventilation procedures recorded
- Ventilatory parameters: PaO₂/FiO₂, FiO₂, tidal volume (TV), respiratory rate (RR), static compliance (Cstat), dynamic compliance (Cdyn), PEEP (positive end-expiratory pressure), PIP (peak inspiratory pressure), Plateau Pressure (Pplat)
- Vital signs will be obtained as appropriate
- AEs review (including SAEs)
- Concomitant medications and procedure review as applicable
- Discharge date from ICU if applicable

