7.2.2 Closed suction tracheal aspirate (TA) samples

Closed suction tracheal aspirate (TA) samples will be taken before the first surfactant dose and after 12, 24, 48, 72, 96h and relative timepoints in the control group since randomisation.

The subsequent samples will be used for the mechanistic studies outlined above ([section 2](#)) and will assess the efficacy of surfactant administration.

The TA samples will consist of blind suctioning by a cannula introduced through a port into the endotracheal tube. A volume of 20-50 ml saline will be administered, with an estimated recovery of 8-10 ml. This procedure will not interrupt the ventilator circuit and will not result in desaturation.

Clinical Study Code No.: CLI-050000-04	Version No.: 4.0
EUDRACT No.: 2020-002632-75 – IND No: 153286	Date: 02 MAR 2021

Blind suctioning following the administration of small volumes of saline is routine practice for the clearance of secretions in ventilated patients.

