7.2.3 Laboratories involved

The above-mentioned analysis is a part of the standard care for these patients and will be carried out by local hospital laboratories. Specific assessments concerning to the mechanistic investigations will be performed at the University College London laboratory and at Imperial College, London.

The sample collection, processing storage and shipment for analysis will be described in a laboratory manual.

These exploratory parameters will be assessed only on UK patients enrolled in the study. Given the current pandemic situation and the samples delivery procedure within 48h, it has been deemed appropriate to avoid additional burden for American sites.

Surfactant lipid composition and concentration (University College London)

Mass spectrometric analysis of molecular species compositions of phosphatidylcholine (PC), sphingomyelin (SM), phosphatidylglycerol (PG) and phosphatidylinositol (PI) in small volume BAL samples. It would be expected a reduced surfactant concentration and altered composition in baseline samples taken immediately before surfactant administration. These would both change after surfactant is given, and the aim is to assess the ratio of exogenous to endogenous surfactant from these two different compositions [31][32].

Analysis of sequential samples will provide an indication of exogenous surfactant turnover. Liquid Chromatography with Mass spectrometric analyses will also be performed to establish corresponding lipidomic profiles of matching plasma and airway samples, that will include analyses of related lipid species and lipid derived inflammatory mediators.

Surfactant function (Imperial College, London)

Surfactant function will be determined by measuring surfactant adsorption to the air: liquid interface in a Langmuir trough. The tensioactive properties of lung surfactant from patients' BAL will be measured. It will be investigated whether isolated surfactant will have compromised function by the inhibition of plasma proteins, and whether the function can be recovered after administration of supplemented surfactant. Maximum reduction of the surface tension over continuous compression: expansion cycles models the physiological breathing cycles of intubated patients and will be carried out on a captive bubble surfactometer or similar device. Adsorption analysis of the equilibrium surface tension, together with kinetics of the process, will explore inhibition processes in surfactant function.

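### The SAP anchors baseline to randomisation in controls but to first dose in the poractant arm, which leaves a one-sided opening for a post-allocation baseline

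*SAP*

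**What the plan says.** SAP 7.9.1 gives a different cut-off for each arm: "Baseline is defined as the last non-missing value available before randomisation (for control group)/first treatment dose (for poractant alfa group". Change from baseline is the later value minus this one.

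Four protocol statements determine what can fall between the two cut-offs:

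- **Gap to dosing.** Section 7.1.2 says that in the poractant arm "the treatment must start soon after the randomization (max 2 hr), and within 48hr after intubation".
- **Oxygen.** Section 6.2.3 says "Before treatment, patients transiently will receive 100% oxygen". It does not say when this starts or how long it lasts.
- **Blinding.** Section 6.6 says "This is an open-label study", so staff know the arm throughout the gap.
- **Schedule.** In the Section 7.1 table, the general column header for the treated arm reads "Before randomisation/treatment and 6-12-24h after each administration up to 72 hours". The specific rows for arterial blood gas and for ventilator parameters read "Before randomisation and 6-12-24h after each administration up to 72 hours".

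Two further SAP rules bear on an extra value. Section 7.11 presents data at the nominal timepoint and sends unscheduled values to review before database lock. Section 7.12 says that everything in the database is used. Neither says what to do with a value taken after randomisation but before the first dose, or with one taken on 100% oxygen.

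**The concern.** In a randomised comparison, baseline should be defined alike in both arms and fixed before allocation is known. Here the control arm's cut-off closes at randomisation and the poractant arm's stays open for up to 2 hours more. Those hours include a step that only treated patients undergo and that raises FiO2 by design. Whether an extra value is recorded then may itself depend on the arm.

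A treated baseline recorded on 100% oxygen would make FiO2 appear to fall without any drug effect. The same baseline feeds the change in PaO2/FiO2, the >20% responder endpoint, severity improvement, SOFA, ventilator and blood gas changes, vital signs and laboratory values. Recruitment stopped short of 70 and the SAP now reports descriptive summaries only. These means and percentages therefore form much of the secondary efficacy evidence, and in a small sample a few displaced baselines carry weight.

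The rule also leaves a gap. A patient randomised to poractant but never dosed can be in the ITT set (SAP 6.2), yet has no first dose from which to define baseline.

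**Working it through.** **1. The plan's own figure.** The only design figure is 84% power for ventilator-free days (Protocol 12.1: 42 vs 28 patients, difference 4 days, SD 5.5, two-sided 0.05).

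- Standardised difference: 4 / [5.5 x sqrt(1/28 + 1/42)] = 4 / 1.342 = 2.98.
- Normal approximation: Phi(2.98 - 1.96) = 84.6%. Noncentral t with 68 df: 83.6%. Both agree with 84%.
- No baseline value enters, so neither the problem nor the fix changes this figure.

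**2. Is a value scheduled in the gap?** Not for the oxygenation endpoints. The blood gas and ventilator rows, and Protocol 7.2.1.1 for blood gas, put the treated-arm value before randomisation. SOFA, vital signs and safety laboratory tests have their pre-treatment value at screening, and all screening procedures must be complete before randomisation. The permitted time deviations apply to post-dose times only. A value in the gap would therefore be extra or late. The looser column header does not rule one out.

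**3. FiO2.** The documents give no usual FiO2 and no share of patients measured on 100% oxygen, so both are assumed. With no true change, shift in arm mean = -share x (100 - usual FiO2):

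| Share on 100% oxygen | FiO2 60% | FiO2 70% | FiO2 80% |
|---|---|---|---|
| 0% (schedule followed) | 0 | 0 | 0 |
| 10% | -4 | -3 | -2 |
| 25% | -10 | -7.5 | -5 |

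Each affected patient shifts by -40 to -20 points. The sign is fixed: it can only favour poractant.

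**4. PaO2/FiO2.** Let f be the usual FiO2 as a fraction and g the factor by which PaO2 rises on 100% oxygen (assumed). The recorded baseline is k = g x f times the true one. With no true change, the apparent change is 1/k - 1:

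| PaO2 response | f = 0.6 | f = 0.8 |
|---|---|---|
| No rise (g = 1) | k = 0.6, +67% | k = 0.8, +25% |
| In proportion (g = 1/f) | k = 1, 0% | k = 1, 0% |
| Doubles (g = 2) | k = 1.2, -17% | k = 1.6, -38% |

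**5. Responder and severity.**

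- Responder: if PaO2 does not rise, an unchanged patient counts as a >20% responder (+67% or +25%). If PaO2 doubles, the true gain needed is 1.2k - 1, which is 44% at k = 1.2 and 92% at k = 1.6, so real responders are missed.
- Severity: at k = 0.8, a true ratio from above 100 up to 100/0.8 = 125 is recorded as severe rather than moderate, which creates a spurious later improvement. At k = 1.2, a true ratio above 100/1.2 = 83 and up to 100 is recorded as moderate, which hides one.

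**6. Exploratory samples.** Protocol 7.2.2 says "Closed suction tracheal aspirate (TA) samples will be taken before the first surfactant dose", Section 2.3 gives the same timing, and the lipid analysis in 7.2.3 refers to "baseline samples taken immediately before surfactant administration". The mechanistic row of the schedule table says before randomisation. With up to 2 hours between the two events, these are not the same instruction.

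**The case against.** The strongest reply is that the problem does not arise if the trial is run as scheduled. The rows for the exposed oxygenation measurements are specific and pre-randomisation in both arms. SAP 7.11 favours the nominal timepoint and has unscheduled values reviewed before lock. Treated-arm follow-up times run from dosing, so a pre-dose baseline matches that arm's time origin. The primary endpoint is untouched and nothing is tested.

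Most of this stands. A reader might infer that 7.9.1 forces a value from the gap to be used, or overrides the schedule. Section 7.11 prevents that reading: what the SAP leaves is ambiguity about an extra pre-dose value, since 7.9.1 takes the latest one and 7.12 excludes nothing. A reader might also infer that some treated baselines were in fact taken on 100% oxygen. The documents do not show this.

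The time-origin argument does not rescue the rule. Follow-up may be timed from dosing, but a between-arm comparison still needs baselines defined alike and before allocation. If no value exists in the gap, a common rule changes nothing. If one exists, the common rule keeps it out.

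**Conclusion.** The asymmetry is on the face of SAP 7.9.1, and no SAP rule closes it. It opens a possible route to bias; it is not a demonstrated bias.

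The size for mean FiO2 change is 0 to -10 percentage points in favour of poractant. Zero applies if the schedule was followed. The upper end rests on two assumptions: 25% of treated patients with a baseline recorded on 100% oxygen, and a usual FiO2 of 60%. It is tempting to extend the direction to PaO2/FiO2, the responder endpoint and severity improvement. The arithmetic does not support that: they can move either way, or not at all if PaO2 rises in proportion.

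Nor does the point amount to a broken randomised comparison overall. Ventilator-free days, the key secondary endpoint and mortality use no baseline value. The exposure is confined to descriptive summaries of baseline-dependent secondary, exploratory and safety variables. A specific correction to the definition is still worth making, because it is nearly free.

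**What to change.** In SAP 7.9.1, for FiO2, PaO2/FiO2, blood gas, ventilator, SOFA, vital sign and safety laboratory data, define baseline in both arms as the last non-missing value before randomisation. List values taken between randomisation and first dose, but do not use them as baseline. This also gives a baseline to patients allocated to poractant but never dosed.

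Do not apply the rule to tracheal aspirates as it stands. First reconcile Protocol 2.3, 7.2.2 and 7.2.3 with the mechanistic row of the schedule in 7.1. Where a pre-dose aspirate taken after randomisation is the only one, keep it as baseline; a blanket cut-off could leave treated UK patients with no aspirate baseline.

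If the SAP can no longer be amended, state the rule in the study report, with the number of treated patients whose baseline falls after randomisation. If that number is zero for the oxygenation data, the point is closed for those endpoints.

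The cost is one SAP sentence plus a separate rule for exploratory samples, which is the small downside. The sample size of 70 and the 84% power are unchanged.

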7.9.2 Date of First and Last Study Medication Administration

The date of first study medication administration is the earliest date of study medication administrated considering the eCRF data, corresponding to the date part of the variable RFXSTDTC in the study data tabulation model (SDTM) dataset DM.

The date of last study medication administration is the latest date of study medication administrated considering the eCRF data, corresponding to the date part of the variable RFXENDTC in the study data tabulation model (SDTM) dataset DM.

7.9.3 Study Day

If not otherwise specified, all assessment days will be related to date of randomization.

The randomization date is referred to as Day 1.

- If the date of the assessment is on or after the randomisation, then
Study Day = (date of assessment – randomisation date) + 1.
- If the date of the assessment is prior to the randomisation, then
Study Day = (date of assessment – randomisation date).

7.9.4 Visit Dates

For each visit, the variable SVSTDTC in the SDTM SV dataset will be considered as the visit date in all the algorithms and the listings. SVSTDTC corresponds to the minimum of all assessment dates performed for a visit.

ATPT variable derived in ADaM datasets will be considered for the timepoint analyses. In the listings, --TPT variables of SDTM datasets will be used unless specified otherwise.

For the end of randomized treatment date, if the visit end date (SVENDTC) is different from the visit start date (i.e. at least one day after) (SVSTDTC) and if the subject is still under randomized treatment, the end of randomized treatment date will be SVENDTC.

7.9.5 Duration of Adverse Events or Medications

The duration of an AE or medication will be calculated as follows:

- AE/Medication End date – AE/Medication Start date + 1 (when both dates are completely known);
- Date of study completion/discontinuation – AE/Medication Start date + 1 (when the start date is fully known but the AE or medication still ongoing at the end of the trial): in this case the duration will be presented as “>x” days in the listing rather than “x” days;

- Missing (when the start date is incomplete or unknown, or when the AE or medication ended but with an incomplete or unknown end date, or when the start date is greater than date of study completion/discontinuation).

7.10 Diary Data

Not applicable. Diary data are not collected in this study.

7.11 Data Re-allocation and duplication

In general, for by timepoint summaries, data recorded at the nominal timepoint will be presented. Data collected at unscheduled timepoints will be reviewed during the review of the data before database lock. Any re-allocation of unscheduled data will be described and justified in the Data Review Report, which will be finalized prior to database lock. In any case, listings will include scheduled, unscheduled and early discontinuation data.

Duplicated data reported twice at 2 different timepoints will be reported only once in both listings and tables at the first occurrence for post dose/post randomization and the last occurrence for pre dose/ pre randomisation.

7.12 Exclusion of Data from the Statistical Analyses

All data collected in the database will be used in all statistical analyses.

7.13 Listings

All data collected in the eCRF will be presented in the individual listings. All listing will be presented for the ITT set (equal to the randomised set), unless otherwise specified.

7.14 Coding

Medical and surgical history, concomitant diseases, procedures and adverse events will be coded according to Medical Dictionary for Regulatory Activities (MedDRA) version 23.0 or higher.

Medications will be coded using the World Health Organization Drug Dictionary (WHO-DD) version March 2020 or later.

8 Study Population

8.1 Disposition of Subjects and Discontinuations

8.1.1 Disposition of Subjects

The number of subjects screened, randomised will be presented by country, site and treatment group.

A flow chart will be produced.

8.1.2 Discontinuation from the Study

The number and percentage of subjects who completed the study, withdrew from the study, and the reason for withdrawal from the study will be presented by treatment group and overall.

An individual subject listing will be provided for the disposition data.

8.1.3 Protocol Deviations and Analysis Sets

All important clinical deviations, including Good clinical Practice (GCP) ones, will be discussed during Data Review meeting to evaluate impact on analyses population and described in the Data Review Report.

The following categories will be classified as important protocol deviations:

- Discontinuation
- Inclusion/Exclusion Criteria
- Informed Consent
- Safety Reporting
- Study Intervention
- Trial Procedures

Other categories may be added and will be discussed during the DRM and documented in the DRR before the data base lock.

All important clinical deviations will be summarized by treatment group and overall.

The number of subjects included in the ITT set, in the Safety Set will be summarised for each treatment and overall using the Enrolled Set.

